### 5.10.1. Health Economics

Health economic outcome measures to be recorded will include:

- Work status, work-days missed and ability to do their work the year prior to baseline, and at the 1- and 2 Year visits
- Health care utilization (office visits, hospital visits, emergency room visits, and other therapies such as physical therapy) the year prior to baseline and at the 1- and 2 Year visits

### 5.10.2. Activity Data Collection

Activity data will be collected on a subset of patients who:

- have an activity tracker that they have used regularly for at least three months,
- agree to wear the activity tracker for the duration of the study, and
- agree to have activity data transmitted to be saved in the database.

After signing consent and meeting enrollment criteria, activity data from at least 2 weeks prior to enrollment will be downloaded. Activity data will be collected continuously while the patient is wearing the activity tracker and downloaded periodically by the patient. To help ensure complete data are obtained, a download of the data will also occur at each study visit.

The time period from Baseline through Activation will serve as the Baseline assessment of activity, with the following exceptions:

- Patients in the Treatment group would be expected to be moving less during the healing process post-procedure; therefore, activity data will be excluded between the Implant and Activation visits (approximately 2 weeks).
- Patients in the Control group will have the 2-week time period prior to Activation excluded to align with the timeframe excluded for the Treatment group.

Activity data to be collected include:

- Distance and Number of Steps
- Stationary Time
- Sleep Data

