Additional Supporting Analyses	
 
Comparison between Treatment and Control in the of responder rate in ODI at 1 year, where a change ≥15 points is considered a responder
 
Comparison between Treatment and Control in the cumulative proportion of responder rate in ODI at 1 year
 
Comparison between Treatment and Control in the of responder rate in NRS at 1 year, where a change ≥50% is considered a responder
 
Comparison between Treatment and Control in the cumulative proportion of responder rate in NRS at 1 year, where a change ≥50% is considered a responder
 
Comparison between Treatment and Control in the cumulative proportion of responder rate in NRS at 1 year
 
Within group changes in all analyses will be assessed at 2 years
 
Cost-effectiveness assessment including:         
 
Change in work status, work-days missed and ability to do their work at 1 and 2 years compared to baseline
 
Health care utilization (office visits, hospital visits, emergency room visits, and other therapies such as physical therapy) at 1 and 2 years compared to baseline
 
 
 
Activity monitoring, including the number of steps and amount of sleep, will be collected on a subset of patients and assessed through 2 years compared to baseline
 
Additional ad hoc analyses may also be conducted
 
		

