## 3.2. Study Visits and Data Collection Schedule

The study visit schedule is provided in Table 3. The study visit schedule will vary slightly between the groups to account for the Treatment group being implanted after the randomization visit. For the Treatment group, visit timing for all visits will be based on Activation. For the Control group visit timing through the 1-year visit will be based on Randomization. After those in the Control group are implanted, the timing of the remaining visits will be based on the Activation visit.

Visit	Treatment	Control
Informed consent, baseline	$\checkmark$	✓
Randomization (Approx. 14 days post baseline)	$\checkmark$	✓
ReActiv8 implant (Approx. 14 days post randomization)	$\checkmark$	
Activation (Approx. 14 days post implant)	$\checkmark$	
1.5-month (45 ± 14 days)	$\checkmark$	$\checkmark$
3-month (90 ± 30 days)	$\checkmark$	$\checkmark$
6-month (180 ± 30 days)	$\checkmark$	$\checkmark$
1-year (365 ± 60 days)	$\checkmark$	$\checkmark$
ReActiv8 implant (within 60 days of the 1-year visit)		$\checkmark$
Activation (Approx. 14 days post implant)		$\checkmark$
13.5-month (410 ± 14 days)		$\checkmark$
15-month (450 ± 30 days)		$\checkmark$
18-month (540 ± 30 days)	$\checkmark$	$\checkmark$
2-year (730 ± 60 days)	$\checkmark$	$\checkmark$

Table 3: Visit S	chedule with	Recommended	Visit Windows
	Sheadle with	Reconnicitaca	

A summary of the data collection schedule is shown for the Treatment group in Table 4 and for the Control group in Table 5.

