### 5.10. Supporting Analyses

The supporting efficacy analyses will include:

- Comparison between the Treatment and Control groups in the of responder rate in ODI at the 1 Year visit, where a change ≥15 points is considered a responder
- Comparison between the Treatment and Control groups in the cumulative proportion of responder rate (a comparison of ranks of the percentage of "responders" across the range of all possible response thresholds) in ODI at the 1 Year visit,
- Comparison between the Treatment and Control groups in the of responder rate in NRS at the 1 Year visit, where a change ≥50% is considered a responder
- Comparison between the Treatment and Control groups in the cumulative proportion of responder rate (a comparison of ranks of the percentage of "responders" across the range of all possible response thresholds) in NRS at the 1 Year visit
- Within group changes in all analyses will also be assessed at the 2 Year visit
- Health economic outcome measures at the 1- and 2 Year visits will be compared to baseline
- Activity monitoring will be collected on a subset of patients and assessed through the 2 Year visit and compared to baseline
- Additional ad hoc analyses may also be conducted.

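### The activity baseline runs to Activation, which Control patients reach only after an optional implant following the 1-year visit, so the Control baseline absorbs the whole randomized year

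*SAP*

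**What the plan says.** SAP 5.10.2 and Protocol 3.1.7 carry the same sentence, without limiting it to one arm: "The time period from Baseline through Activation will serve as the Baseline assessment of activity". Two exclusions follow. Treatment patients lose the days between implant and Activation, about 2 weeks. Control patients lose the 2 weeks before Activation, "to align with the timeframe excluded for the Treatment group". Both sections also provide for downloading at least 2 weeks of tracker data from before enrollment, but neither says whether those days count as baseline.

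On use, SAP 5.10 states "Activity monitoring will be collected on a subset of patients and assessed through the 2 Year visit and compared to baseline", and the protocol synopsis (Table 1) likewise says activity "will be collected on a subset of patients and assessed through 2 years compared to baseline".

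On timing, Protocol 3.2 has different anchors for the two arms: "For the Treatment group, visit timing for all visits will be based on Activation", but "For the Control group visit timing through the 1-year visit will be based on Randomization". In Table 3 the Control column has no Activation until after the entry "ReActiv8 implant (within 60 days of the 1-year visit"). Table 5 gives the same order. It also schedules Control activity downloads at 1.5, 3 and 6 months and at 1 year, all before any Control Activation. Protocol 3 and SAP 3 state that Controls who do not take the device exit after the 1-year visit.

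**The concern.** A baseline should close before the period in which change is to be measured. In the Treatment arm it does, because the window ends before the device is switched on. In the Control arm the closing event lies beyond the end of the randomized comparison and happens only for patients who choose the implant.

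Three consequences follow:

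- The four scheduled Control downloads through 1 year all supply baseline data. There is no Control period before the 1-year visit that is follow-up and not also baseline.
- For later-implanted Controls a change at 1 year can still be calculated, but the reference period contains the same year, so most of any real shift cancels.
- For Controls who decline the implant, the baseline has no defined end.

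If activity changes were shown side by side at 1 year, the arms would be measured against very different references. Two programmers working from the same sentence could also arrive at about 28 or about 400 baseline days.

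**Working it through.** The plan gives no figure for the length of the activity baseline, so there is none to reproduce. The lengths below follow from Protocol Table 3, in days counted from Randomization.

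**Inputs**

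- Baseline visit: about 14 days before Randomization, so day −14.
- Treatment implant: about day 14. Treatment Activation: about 14 days later, day 28.
- Control 1-year visit: day V, from the entry "1-year (365 ± 60 days"), so V = 365 with a range of 305 to 425.
- Control implant: d days after that visit, with d from 0 to 60.
- Control Activation: about 14 days after implant, so day V + d + 14.
- Exclusion: 14 days before Activation in each arm.

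**Treatment baseline**

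(28 + 14) − 14 = 28 days, all before implant.

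**Control baseline, implanted patients**

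(V + d + 14 + 14) − 14 = V + d + 14 days.

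| V | d | Control baseline days | Ratio to Treatment (28) |
|---|---|---|---|
| 365 | 0 | 379 | 13.5 |
| 365 | 60 | 439 | 15.7 |
| 305 | 0 | 319 | 11.4 |
| 425 | 60 | 499 | 17.8 |

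Only 14 of these days precede Randomization. With V = 365 the share falling after Randomization is 365/379 = 96% to 425/439 = 97%. With no implant delay the excluded fortnight begins at the 1-year visit, so it removes none of the randomized year.

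**Control baseline, patients not implanted**

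There is no Activation, so the window has no end.

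**If the pre-enrollment download counts as baseline**

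Adding 14 days gives 42 for Treatment and 393 to 453 for Control (333 to 513 across the visit window). The conclusion is unchanged.

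**Effect on a 1-year Control change (illustration)**

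Assume that activity shifts by a constant amount at Randomization and that there is no implant delay. The baseline mean then already contains 365/379 of the shift, and the calculated change shows only 14/379, or about 4%. With the 14 pre-enrollment days added it is 28/393, or about 7%.

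**If a parallel early window was intended**

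With a nominal Control Activation at day 28, the window is (28 + 14) − 14 = 28 days, equal to Treatment. No section of either document states such a date.

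**The case against.** The strongest reply is that the rule makes sense as a pre-device reference for each patient. Activation is when stimulation starts. For implanted Controls the excluded fortnight is their own implant-to-Activation healing period, which mirrors the Treatment exclusion. The plan also calls for within-group changes at 2 years, and a pre-device baseline serves that purpose. This stands for post-implant change in implanted Controls, where the baseline is long but coherent. It does not rescue the rule in general: neither document restricts it to that use, and it gives nothing to Controls who are never implanted.

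A second reply is that no between-arm activity contrast is specified. Other bullets in SAP 5.10 name a Treatment versus Control comparison and the activity bullet does not. Visit downloads are there to secure complete data, so their schedule says little about what counts as follow-up. Recording is continuous, so any window could be derived later. All of this is fair and limits the consequence. Even so, a change from baseline in Control during the randomized year cannot be formed properly under the stated rule, and a window chosen after the data are seen is a post hoc choice.

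Third, the day ranges are not hard bounds. Protocol 5 treats visit windows as guidance, so 319 to 499 days illustrates the recommended schedule only. That is accepted; the point does not depend on the exact length.

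**Conclusion.** The concern holds. As written, the activity baseline is about 28 days in Treatment. In later-implanted Controls it is about 379 to 439 days (319 to 499 across the recommended 1-year window), and in Controls who exit at 1 year it has no end. The wording of the Control exclusion suggests that a parallel window may have been meant, but neither document defines the date it would need.

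The figures assume the nominal Table 3 intervals, a Control implant 0 to 60 days after the 1-year visit, and counting from the Baseline visit.

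The reach is limited to a supporting analysis in patients who already use a tracker, with no planned between-arm activity test. The primary, secondary and tertiary endpoints and the safety assessment are unaffected. The definition should be corrected before activity data are analysed.

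**What to change.** Amend SAP 5.10.2 and Protocol 3.1.7 together, since both carry the sentence.

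**Preferred.** End the randomized-phase activity baseline at Randomization in both arms. Use the 2 or more weeks already downloaded from before enrollment plus Baseline to Randomization: 14 + 14 = about 28 days, or more where the download is longer, all before allocation. State that Treatment follow-up starts at Activation, so that the roughly 28 days from Randomization to Activation are neither baseline nor follow-up. Leave out the matching 28 days after Randomization in Control.

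**Smaller alternative.** Keep the present rule and define, for this analysis only, a nominal Control Activation date about 28 days after Randomization for every Control, whether implanted later or not. Each arm then has about 28 baseline days.

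Under either option:

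- Summarise activity as daily means, because follow-up to the 1-year visit is about 365 − 28 = 337 days in Control and about 365 in Treatment.
- Analyse post-implant activity in Controls implanted after 1 year separately, against a stated pre-implant window, with their implant-to-Activation days excluded.

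**Cost.** No new data are needed. The change requires a SAP revision and a minor protocol amendment under Protocol 8.1, with sponsor and investigator agreement, a recorded justification and local approval such as IRB submission. The preferred option gives up about 14 pre-implant Treatment days as baseline. The alternative leaves about 14 baseline days in each arm after allocation. Both set aside about 28 Control days after Randomization as not follow-up.

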### 5.11. Subgroup Analyses and Predictors of Response

The primary efficacy endpoint will be analyzed in the subgroups defined below to demonstrate consistency of treatment effect. The specified MMRM model will be used to test the interaction of randomization assignment and subgroup/covariate. Subgroups to be analyzed will include, at a minimum:

- Gender
- Age (as both a continuous variable and grouped in ranges)
- Ethnicity
- Baseline NRS
- Baseline EQ-5D
- BMI (as both a continuous variable and grouped in ranges)
- Duration of work status adversely affected by CLBP

Multivariable analysis to explore predictors of response with response defined as an improvement of 15 points or more in ODI will be conducted in the Treatment group patients. Univariable regression models with (at a minimum) covariates as defined below will be analyzed to determine predictors of response. All covariates with an association with response (p<0.20) will be included in a multivariable logistic regression model.

- Duration of back pain (as both a continuous variable and grouped in ranges)
- Baseline ODI (as both a continuous variable and grouped in ranges)
- Baseline EQ-5D (as both a continuous variable and grouped in ranges)
- Baseline VAS (as both a continuous variable and grouped in ranges)
- Baseline opioid use
- Age
- Gender
- BMI
- Compliance with stimulation (the number of minutes that stimulation was actually delivered divided by the number of minutes that could have been delivered)

<sup>1 Gilligan, C., Rauck, R., Rathmell, J, et al. An Implantable Restorative Neurostimulator for Refractory Mechanical Chronic Low Back Pain - A Randomized Sham Controlled Trial. *Pain* 2021 Oct 1;162(10):2486-2498.

<sup>2 Fairbank, J. & Pynsent, P. B. The Oswestry Disability Index. Spine (Phila. Pa. 1976). 25, 2940–52; discussion 2952 (2000).

<sup>3 Hochberg Y. A sharper Bonferroni procedure for multiple tests of significance. Biometrika 1988;75:800-2. 10.1093/biomet/75.4.800

<sup>4 Verbeke G and Molenberghs G. Linear Mixed Models for Longitudinal Data, New York: Springer 2000.

<sup>5 Rubin DB. Inference and missing data. Biometrika 1976. 63:581-592.

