### 3.2. Sample Size Rationale

The sample size for the study is determined under the following assumptions for the primary efficacy endpoint, which are based on a prior study of ReActiv8, and approximately the MMRM test by its corresponding unadjusted t-test. All else being equal, this is a conservative estimate of power since control for baseline and inclusion of intermediate time points is not accounted for.

- Minimum power of 80%
- Type I error of 5%
- Assumed mean change in Treatment group: 18.2
- Assumed mean change in Control group: 12.2
- Pooled Standard Deviation: 15

Under the above assumptions, a minimum of 204 evaluable patients is required in order to demonstrate superiority of the ReActiv8 treatment. To account for attrition, approximately 230 patients will be enrolled and randomized.

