#### Hypothesis Test

The primary superiority hypothesis is that the mean change in ODI from baseline to 1 Year is more negative (i.e., superior to) for patients treated with ReActiv8 Stimulation Therapy compared to patients treated with OMM. Symbolically, the primary effectiveness hypotheses can be represented as follows:

Ho:  $\delta_T - \delta_C \ge 0$ Ha:  $\delta_T - \delta_C < 0$ 

Where  $\delta_T$  and  $\delta_C$  are the true mean changes in ODI from baseline to 1 Year for ReActiv8 Stimulation Therapy (T) and for patients treated with OMM alone (C), respectively. See section 5.7 for a discussion on Mixed Model Repeated Measures. See discussion in Section 5.8 defining the definition of the primary estimand  $\delta_T - \delta_C$ .

The two-sided p-value for the equality null hypothesis will be reported as well as the two-sided adjusted 95% confidence interval for the difference in mean changes. Superiority will only be claimed if p<0.05 and the mean change is more negative (greater improvement) for the Treatment group compared to the Control group. This is equivalent to specifying a one-sided test at  $\alpha$ =0.025.

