### 5.7. Mixed Model for Repeated Measures

These hypotheses will be tested using the 1 Year contrast estimated from a mixed model for repeated measures (MMRM) (Verbeke and Molenberghs 2000). The MMRM will include baseline endpoint value (ODI, NRS or EQ-5D), treatment group, visit, and visit by treatment group interaction. Changes from baseline to Months 1.5, 3, and 6, as well as from baseline to 1 Year are included in the MMRM as a function of the fixed effects. A random site effect will be included to account for the randomization within site. A random site effect is appropriate as we wish to generalize to patients from any site and specifically from sites included in this study. Patients lost-to-follow-up due to reasons related to lack of effectiveness or subsequent to a related AE will utilize baseline observation carried forward imputation of missing values; otherwise, missing values are implicitly imputed while estimating the parameters of the MMRM. MMRM produces unbiased estimates when there is missing follow-up when missing-at-random (MAR) assumption is true (Rubin 1976). The MAR assumption is that the likelihood of missing is statistically independent of the distribution of the unobserved missing outcome conditional on observed data and is most reasonable for missingness not associated with lack of efficacy.

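### SAP 5.11 sets out to show a consistent treatment effect, but the only inferential method it names is an interaction test too imprecise for a non-significant result to show that

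*SAP*

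**What the plan says.** SAP 5.11 opens with its aim: "The primary efficacy endpoint will be analyzed in the subgroups defined below to demonstrate consistency of treatment effect". The next sentence gives the method: "The specified MMRM model will be used to test the interaction of randomization assignment and subgroup/covariate". At least seven factors follow: gender, age, ethnicity, baseline NRS, baseline EQ-5D, BMI and duration of affected work status. Age and BMI are each taken in two forms, continuous and grouped, which makes at least nine tests.

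The section does not state a significance level for the interaction, a margin within which effects would count as consistent, an interval for the difference between subgroups, or how to read a non-significant result.

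The model it refers to is in SAP 5.7: "The MMRM will include baseline endpoint value (ODI, NRS or EQ-5D), treatment group, visit, and visit by treatment group interaction". That section tests its hypotheses with the 1 Year contrast. SAP 5.11 does not say whether the subgroup interaction is also taken at 1 Year.

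The sample size in SAP 3.2 addresses the overall comparison only: "Under the above assumptions, a minimum of 204 evaluable patients is required in order to demonstrate superiority of the ReActiv8 treatment".

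**The concern.** Consistency is an equivalence-type conclusion: the effect is claimed to be similar across subgroups. A significance test of interaction takes similarity as its null hypothesis. Failing to reject it supports similarity only if the test would probably have detected a difference worth knowing about. With this aim, this test and no margin, a non-significant p-value is the result most likely to be reported as demonstrating consistency.

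The device is implanted permanently. A report could say that it works alike in men and women, in older and younger patients, or across BMI, although one group gains little. The primary result is not affected. What is at stake is a secondary statement about who benefits.

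**Working it through.** **Inputs from the documents.** SAP 3.2: SD 15; mean changes 18.2 and 12.2, so a difference of 6; 204 evaluable; 80% power; 5% type I error. SAP 5.4.1 makes the primary test two-sided at 0.05. SAP 3.1: 1:1 allocation.

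**Assumptions.** Interaction level two-sided 0.05, varied to 0.15. Subgroup split 50/50 to 80/20, with 1:1 arms within each level. Target difference 0.5 SD = 7.5 points, which exceeds the assumed overall effect. The SD is also tried at 12 to allow for baseline adjustment.

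**Step 1: the plan's own figure.** n per arm = 2 × [15 × (1.960 + 0.842) / 6]² = 98.1, so 99 per arm and 198 in total. A noncentral t calculation gives 200. Both are within 3% of 204. At 102 per arm the main-effect SE is 15 × √(2/102) = 2.10 and power is 81.5%. The stated size is reproduced.

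**Step 2: standard error of the interaction.** For a two-level factor with share f in one level:

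SE = (2 × SD / √N) × √(1/f + 1/(1 − f))

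- f = 0.5: (30 / 14.283) × 2 = 4.20
- f = 0.8: (30 / 14.283) × 2.5 = 5.25

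With equal subgroups this is twice the main-effect SE.

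**Step 3: miss rate for a 7.5-point difference.** Miss rate = 1 − [Φ(7.5/SE − z) + Φ(−7.5/SE − z)].

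- f = 0.5: 7.5/4.20 = 1.785; power 43.1%, missed 56.9%
- f = 0.8: 7.5/5.25 = 1.428; power 29.8%, missed 70.2%

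The t versions give 57.3% and 70.5%.

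**Step 4: sensitivity, 7.5-point difference.**

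| SD | N | Two-sided level | Missed, 50/50 | Missed, 80/20 |
|---|---|---|---|---|
| 15 | 204 | 0.05 | 57% | 70% |
| 15 | 230 | 0.05 | 53% | 67% |
| 15 | 204 | 0.10 | 44% | 58% |
| 15 | 204 | 0.15 | 36% | 50% |
| 12 | 204 | 0.05 | 39% | 57% |
| 12 | 204 | 0.15 | 21% | 36% |

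For the last row, SE = 0.8 × 4.20 = 3.36 and 0.8 × 5.25 = 4.20, with z = 1.440. The ratios 7.5/SE are 2.23 and 1.785, giving 21% and 36%.

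**Step 5: other views of the same imprecision (SD 15, N = 204, level 0.05).**

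- A 6-point difference between subgroups, as large as the whole assumed effect, is missed 70% (50/50) to 79% (80/20) of the time.
- If 30% of patients gain nothing and the overall effect is still 6, the others gain 6/0.7 = 8.57. With SE 4.58 this is missed 54% of the time. If 20% gain nothing, the others gain 6/0.8 = 7.5, missed 70%.
- The difference detectable with 80% power is 2.80 × SE = 11.8 to 14.7 points.
- The 95% half-width is 1.96 × SE = 8.2 to 10.3 points. At SD 12 it is 6.6 to 8.2, still above 6.
- 80% power for 7.5 points at 50/50 would need 16 × (15 × 2.802 / 7.5)² ≈ 503 evaluable patients.

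**The case against.** The strongest reply has four parts.

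1. **No rule equates non-significance with consistency.** This is true of SAP 5.11; the link is inferred from the stated aim and the only test named. The inference is reasonable. SAP 4.4 uses that logic openly for sites, treating data as poolable when the interaction p-value is at least 0.15.

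2. **Subgroup estimates may already be intended.** Analysing the primary endpoint within subgroups can fairly be read to include subgroup effects with the 95% interval that SAP 5.4.1 requires. This stands, so it would be wrong to say that the plan excludes subgroup estimates. No interval for the difference between subgroups is mentioned, and that is the quantity that bears on consistency.

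3. **The miss rate depends on unstated inputs.** This also stands. SAP 5.11 gives neither a level nor subgroup sizes. The general 5% statement sits in SAP 5.5, on secondary endpoints, and the 0.15 in SAP 4.4 concerns sites only. SAP 3.2 itself calls its unadjusted calculation conservative. A reader might take 57% to 70% as a property of the plan; it is one end of a range that reaches down to about 21%. It also applies only to two-level factors, not to continuous age or BMI.

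4. **Low interaction power is usual, and no formal claim rests on subgroups.** This is correct and limits the severity. It does not justify an aim of demonstration, and this paragraph is not labelled exploratory.

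Two stronger readings are tempting. A reader might infer that the interaction has no visit component and so averages over Months 1.5, 3, 6 and 1 Year. The documents do not establish this: SAP 5.11 lists no model terms and refers to the primary endpoint, so a 1 Year contrast is at least as natural. The text is open, not wrong. A reader might also infer a 37% chance of at least one false-positive interaction (1 − 0.95⁹). That assumes nine independent tests at 0.05, whereas the two forms of age, and of BMI, are closely related. It is only an upper illustration.

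**Conclusion.** The concern holds in this form: the aim in SAP 5.11 cannot be met by the inferential method it names. For two-level subgroups, a difference larger than the assumed overall effect is missed 57% to 70% of the time with the SAP's SD and evaluable sample size at an assumed 0.05 level. It is still missed 21% to 36% of the time under the most favourable combination tried. In every case examined, the interval on the between-subgroup difference extends more than 6 points either side of the estimate. A non-significant interaction would therefore be compatible with a difference as large as the effect the trial was designed to find.

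The numbers rest on the assumed level, splits and target difference. The conclusion does not depend on any single one of them. The point should be addressed, but it leaves the primary and secondary tests untouched.

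**What to change.** In SAP 5.11:

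- Replace the consistency aim with that of estimating the 1 Year treatment effect in each subgroup, labelled exploratory.
- Define the interaction as the 1 Year contrast, by adding the treatment-by-visit-by-subgroup term and its lower-order terms to the MMRM.
- Report the 1 Year ODI treatment difference in each subgroup, and the difference between subgroups, each with a 95% confidence interval.
- State that interaction p-values are descriptive and unadjusted for multiplicity, and that a non-significant interaction is not evidence of consistency.

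The cost is SAP wording and a few lines of model code, with no new data or patients. The report could no longer claim demonstrated consistency, and the intervals would be wide, at about ±8 to ±10 points on a between-subgroup difference at SD 15.

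### The predictors-of-response analysis in SAP 5.11 uses only a 15-point ODI responder outcome; adding a model of the full ODI change would detect weak to moderate predictors more often

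*SAP*

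**What the plan says.** SAP 5.11 plans two kinds of analysis. The first tests treatment-by-covariate interactions in the primary MMRM, so it uses ODI change on its full scale and both arms. The second, which is the subject here, looks for predictors within the Treatment group: "Multivariable analysis to explore predictors of response with response defined as an improvement of 15 points or more in ODI will be conducted". It lists nine covariates as a minimum. Each is first examined univariably, and then "All covariates with an association with response (p<0.20) will be included in a multivariable logistic regression model".

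SAP 5.4.1 ties the 15-point figure to a cited minimally important change. SAP 5.8 and 5.10 use the same cut as the responder definition. SAP 5.8 otherwise treats responder analyses as a fallback if the MMRM assumptions fail, and as a descriptive comparison between groups. The documents state no sample size or power for the predictors analysis, and neither document plans a within-arm model of continuous ODI change on these covariates.

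**The concern.** One-year ODI change is continuous, is the primary endpoint, and is analysed on its full scale everywhere that the SAP makes a formal inference. In the predictors analysis alone, the cut version drives both covariate selection and the final model. Cutting at 15 treats improvements of 14 and 16 points as opposites and improvements of 16 and 40 points as the same.

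At the planning values the cut lies close to the centre of the Treatment distribution. That is the least wasteful place for a cut, but the loss is still large. What is at stake is the chance that an exploratory analysis picks up the modest patient characteristics that it is meant to look for, in a group of only about 100 patients.

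**Working it through.** **Inputs.** From SAP 3.2: "Assumed mean change in Treatment group: 18.2", "Assumed mean change in Control group: 12.2", "Pooled Standard Deviation: 15", 80% power, 5% type I error, 204 evaluable and about 230 randomized. SAP 3.1 gives 1:1 allocation. SAP 5.4.1 makes the test two-sided at 0.05 with direction required. The responder cut of 15 and the p<0.20 screen are from SAP 5.11. The correlation r between a covariate and ODI change is not in the documents; 0.15 to 0.40 is assumed.

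**The plan's own figure.** Per arm, n = 2 × 15² × (1.960 + 0.842)² / 6² = 98.1, so 99 per arm and 198 in total. The noncentral t gives 100 per arm, 200 in total. The stated 204 is within 3% of both and gives 81.1% power by the t calculation. It is therefore reproduced. At 1:1, 204 evaluable means 102 Treatment patients, and 230 randomized means about 115. Neither per-arm number is printed in the documents.

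**Expected responders.** c = (18.2 − 15)/15 = 0.213. P(improvement ≥ 15) = Φ(0.213) = 0.584, so about 60 responders and 42 non-responders among 102.

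**Information kept by the cut.** For a normal outcome and a weak predictor, the efficiency of the binary outcome relative to the continuous one is φ(c)² / [p(1 − p)] = 0.390² / (0.584 × 0.416) = 0.626. The loss is 37.4%. On this measure, 102 patients analysed as responders carry the information of 102 × 0.626 ≈ 64 analysed on the full scale (115 carry that of about 72). Over means of 15 to 21 and SDs of 12 to 20 the loss runs from 36% to 42%.

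**Effect on power.** The simulation used n = 102, 5,000 runs per row, one standard normal covariate x, and ODI change = 18.2 + 15[r·x + √(1 − r²)·e]. The linear slope t-test is compared with the likelihood-ratio test of a univariable logistic slope on change ≥ 15.

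| r (assumed) | p<0.05: full scale | p<0.05: binary | p<0.20 screen: full scale | p<0.20 screen: binary |
|---|---|---|---|---|
| 0 | 5.0% | 5.3% | 19.7% | 20.9% |
| 0.15 | 32.4% | 23.1% | 60.0% | 47.2% |
| 0.20 | 52.0% | 37.5% | 76.4% | 63.4% |
| 0.25 | 72.6% | 52.6% | 89.7% | 77.5% |
| 0.30 | 87.9% | 69.6% | 96.8% | 89.0% |
| 0.40 | 98.8% | 92.2% | 99.7% | 98.2% |

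Independent repeats agree within about 2 points, and the gaps are similar at n = 115.

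**Cross-check by formula at r = 0.25.** Full scale: atanh(0.25) × √99 = 0.2554 × 9.95 = 2.54, and Φ(2.54 − 1.96) = 72%. Binary: 2.54 × √0.626 = 2.01, and Φ(2.01 − 1.96) = 52%. Both match the table.

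**The case against.** The planned analysis can be defended. Its stated aim is to explore response, the 15-point cut has a cited clinical basis, and which patients reach a meaningful improvement is a different question from which patients improve more on average. That stands, and it is why the responder model should stay. It does not explain why the full-scale model is absent.

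The MMRM interactions in the same section do use full-scale ODI change, and they cover age, gender, BMI and baseline EQ-5D. They test whether the treatment effect differs between patients, not what predicts improvement within the Treatment arm. Their list also omits duration of back pain, baseline ODI, baseline opioid use and compliance with stimulation. The cover is partial.

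A reader might infer three stronger things, none of which is supported.

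- **That the plan will miss real predictors which the full scale would find.** The loss is one of probability. For r from 0.15 to 0.40, only about 1% to 6% of runs reached p<0.05 on the full scale while failing the binary screen. Strong predictors usually pass either way, and those near r = 0.15 are mostly missed at p<0.05 either way.
- **That the logistic model is overloaded.** Dividing 42 non-responders by nine covariates gives 4.7 each, but SAP 5.11 enters only covariates that pass the screen. With no true predictors about 9 × 0.20 = 1.8 enter, or about 24 non-responders each. With three true predictors at r = 0.25, about 3 × 0.77 + 6 × 0.20 = 3.5 enter, or about 12 each. Grouped or added covariates would raise the parameter count, by an amount that the documents do not fix.
- **That the predictors it reports cannot be trusted.** The row for r = 0 shows near-nominal false-positive rates for both methods. What falls is power.

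**Conclusion.** The point holds as a modest, inexpensive improvement. Restricting the within-arm predictor analysis to the 15-point outcome gives up about 37% of the information at the SAP's planning values. For assumed correlations of 0.15 to 0.30 it costs roughly 9 to 20 percentage points of power at p<0.05 and 8 to 13 points at the planned screen. At 0.40 the cost is about 7 and 2 points.

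These sizes assume that ODI change is normal, that the pooled SD applies to the Treatment arm, that 1-year data are complete, and that one continuous, linearly related covariate is tested univariably. The multivariable step and the categorical covariates were not simulated.

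The analysis is exploratory and lies outside the primary test and the Hochberg-controlled secondary tests, so no primary or secondary conclusion changes.

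**What to change.** In SAP 5.11, add a linear regression of continuous 1-year change in ODI on the same covariates in the Treatment group, for both the univariable and the multivariable steps, with baseline ODI always included. Report it alongside the 15-point logistic model, which is kept for clinical interpretation. Replacing the logistic model outright would change the question being asked and is not needed.

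The cost is a sentence or two of SAP text and one further exploratory model, with no new data or visits. The new coefficients will be in ODI points and not odds of response, so the two sets of results must be read side by side.
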